4. ANALYSIS POPULATIONS

The 3 analysis populations are defined below. Subjects will be analyzed based on the treatment to which they are randomly assigned. Identification of the subjects to be included in each analysis population will be determined prior to database unblinding. The database will be locked and unblinded after the SAP is signed and authorized, there are no outstanding data issues, and the final analysis populations are imported into the study database.

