4.3 Per-Protocol Population

The per-protocol (PP) population is defined as all subjects from the ITT population without any important protocol deviations (see Section 4.5). This supplemental efficacy population will be used to assess robustness of the primary analysis results.

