4.5 Protocol Deviations

Protocol deviations (PDs) will be collected during monitoring visits. Protocol deviations will be placed, but not limited to, into the following categories: prohibited concomitant medications, dosing, enrollment inclusion/exclusion criteria, laboratory, non-compliance, and others which are deemed to be study PDs. Each instance of a PD will be reviewed and determined to be important or minor before the study DBL.

A summary of important PDs will be provided as number (%) of subjects with at least 1 important PD and number (%) of subjects in each category in all randomized subjects. A listing by subject will also be provided that will include all PDs, deviation date, type, and any specific comments related to the deviation.

The following conditions, if met, would constitute an important PD. As such, any subject meeting one or more of these conditions would be omitted from the PP population. Important PDs are not limited to the list below. All protocol deviations within the monitoring report and the clinical database will be reconciled and adjudicated by the clinical team after the study is complete for the identification of all other important PDs.

	Category	Explanation
1	No proof of randomization or subjects mistakenly randomized	At Visit 4, there is no randomization number indicated on CRF field or subject mistakenly assigned randomization number.
2	Subject is non-compliant	Subject is not lost to follow-up and is <75% or >125% compliant with study drug at any point in the study.
3	Prohibited medications taken	Subject took any of the prohibited medications listed in Section 10.3.1 of the protocol during the study from screening through the EOS visit, unless the medication is clinically adjudicated as permissible.
4	Treated subject who did not meet inclusion/exclusion	Subject failed one or more of the inclusion or exclusion criteria listed in Section 8 of the

	criteria	protocol, but continued in the double-blind period of the study.
5	Subject tests positive for substance abuse	Subject has one or more positive urine drug screen test at any visit during the course of the study.
6	Subject is unblinded during study	Subject is unblinded to treatment at any time during the course of the study.
7	Subject receives incorrect treatment	Subject's actual treatment received does not match randomized planned treatment.

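### Three per-protocol exclusion rules in SAP 4.5 run past the Day 15 endpoint, so a child with complete Day 15 data can be dropped for a later event (minor)

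*SAP*

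**What the plan says.** SAP 4.3 defines PP as the ITT population without any important protocol deviation and gives its purpose: "This supplemental efficacy population will be used to assess robustness of the primary analysis results". SAP 7.5.1 repeats the primary ANCOVA on it.

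SAP 4.5 lists seven conditions and says that "any subject meeting one or more of these conditions would be omitted from the PP population". Three of them are not tied to the endpoint:

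- Row 3, prohibited medication: any use of a drug listed in protocol 10.3.1 "during the study from screening through the EOS visit, unless the medication is clinically adjudicated as permissible".
- Row 5, drug screen: "Subject has one or more positive urine drug screen test at any visit during the course of the study". A urine drug screen is scheduled at EOS (protocol 11.5.3; SAP 14.1).
- Row 6, unblinding: "Subject is unblinded to treatment at any time during the course of the study".

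The same section says that "Each instance of a PD will be reviewed and determined to be important or minor before the study DBL". It also provides for adjudication by the clinical team after the study, to identify other important deviations beyond the list. SAP 4 adds: "Identification of the subjects to be included in each analysis population will be determined prior to database unblinding".

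The primary outcome (SAP 7.4.1) uses only the Day 1 and Day 15 classroom sessions.

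**The concern.** A PP analysis asks whether the primary result holds among children whose endpoint data were obtained as the protocol intended. Medication first taken after the last Day 15 session, or a blind first broken then, cannot have changed the Day 15 scores. The use behind a positive EOS screen may also have come after them. Removing such children adds nothing to the robustness check.

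It can also bias that check. Every eligible child was on methylphenidate judged effective (protocol 8.1, inclusions 4 and 5) and had to worsen by at least 30% off it (protocol 8.2, exclusion 2). Study drug ends on Day 14, but stimulants stay prohibited until EOS. A family whose child did badly on Day 15 has a reason to restart early. If that happens, PP membership depends on the outcome: placebo children with poor results leave PP more often, the remaining placebo mean looks better, and the PP difference shrinks.

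**Working it through.** **Gap after the endpoint.** The last dose is on Day 14, and EOS is 7 ± 2 days after it, so Day 19 to Day 23. Counted from Day 15, that is 19 − 15 = 4 to 23 − 15 = 8 days.

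**Which rows reach into the gap.** Row 3 names EOS. Row 5 reaches it through the EOS drug screen. Row 6 reaches it because the study runs to the last visit. Row 2 (compliance) does not, since dosing is over. Row 3 has an adjudication exception without a timing criterion; rows 5 and 6 have none. The post-study adjudication is aimed at other important deviations, so it reads as adding exclusions, not releasing listed ones. The important/minor review of each deviation points the other way, so the text is ambiguous for the listed rows.

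**The plan's own power figure.** Inputs from SAP 2.6: 50 per arm, difference 4.0, SD 5, two-sided 5%. For the two-sample t-test, the noncentrality is 4.0 / (5 × √(1/50 + 1/50)) = 4.0 / 1.0 = 4.0 on 98 degrees of freedom, giving power of 97.7%. This agrees with the stated figure of at least 95%.

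**Row 3, outcome-related restarts (assumptions, since the documents give no rate).** Day 15 change is N(0, 5) on placebo and N(−4, 5) on dasotraline, where the second figure is the SD and lower is better. The probability of restarting a stimulant after Day 15 is expit(a + s × change/5). Here s is 0.5, 1 or 2 in log-odds per SD of worse change, and a is set so that 2% or 5% of all children restart. All who restart are excluded. Means, SDs and numbers per arm among those kept come from numerical integration, and power from the same t-test formula.

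| Restart rate | s | PP difference | PP power |
|---|---|---|---|
| none | – | 4.00 | 97.7% |
| 2% | 0.5 | 3.98 | 97.4% |
| 2% | 1 | 3.93 | 97.3% |
| 2% | 2 | 3.82 | 97.0% |
| 5% | 0.5 | 3.96 | 97.0% |
| 5% | 1 | 3.85 | 96.6% |
| 5% | 2 | 3.63 | 95.7% |

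If adjudication under row 3 cleared half of these children, the difference would be 3.82–3.99 and power 96.9–97.6%.

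**Rows 5 and 6, unrelated to outcome.** The difference stays at 4.0. Losing 1%, 2% or 5% of each arm leaves 49.5, 49 or 47.5 per arm and power of 97.6%, 97.5% or 97.1%.

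**The case against.** Row 3 copies the protocol's own prohibition window (protocol 10.3.1), and both documents define PP as ITT without an important deviation. PP can be read as adherence to the whole protocol, in which case the window is a choice and not a mistake. That stands: there is no contradiction between the documents here, and the point is an improvement.

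Row 3 is also the row with the clearest route to outcome-related exclusion, and it can be adjudicated. Deviation dates are listed and membership is fixed before unblinding. That limits the harm, but adjudicators are given no criterion for use after the endpoint.

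Rows 5 and 6 should add little. The blind may be broken only in an emergency (protocol 7.2.3), and dosing is over by Day 15. A reader might infer that row 5 would catch children who return to their previous treatment, but the drug-screen panel in protocol Appendix III does not list methylphenidate. It does list amphetamines, so a child given an amphetamine-based product after Day 15 could be cleared under row 3 and still meet row 5.

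A reader might also infer that row 3 removes every eligible child, because protocol 10.3.1 bars stimulants from screening while inclusion 4 requires methylphenidate before washout. The documents do not support that outcome: the same section schedules the washout, and the adjudication clause can clear earlier use. The literal wording does, however, rely on that clause.

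**Conclusion.** The point holds as a minor one. As written, rows 3, 5 and 6 allow a child with complete, unaffected Day 15 data to be omitted from PP for an event first occurring in the following 4 to 8 days.

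At an assumed 2–5% restart rate related to the Day 15 result, with all such children excluded, the PP difference is about 3.6–4.0 instead of 4.0 and PP power about 96–97% against 97.7%. The rate and the strength of the relation are assumptions.

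A reader might infer serious distortion of PP by supposing that many children restart. The documents give no rate to support that, so no larger range is quoted. Nor do they support a worry about a spurious positive finding: in this model the shift is toward zero. The ITT primary analysis and its power are untouched.

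**What to change.** Before unblinding, amend SAP 4.5:

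1. Conditions 3, 5 and 6 are important deviations leading to PP exclusion only if the medication use, the drug-screen sample or the unblinding is dated on or before Day 15 (Visit 5). The start of each window is unchanged.
2. Events first dated after Day 15 are classed as not important for the PP definition in SAP 4.3 and protocol 15.2. Because PP is defined through important deviations, changing the windows for PP alone would leave the definitions out of step. Protocol 15.3.3 leaves the definition of important deviations to the SAP.
3. Row 5 does not count a screening positive accepted under the note to exclusion 27.
4. Later events stay in the planned listing, which covers "all PDs, deviation date, type, and any specific comments related to the deviation".

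The post-treatment medication class in SAP 5.1 should not serve as the cut-off, because it begins after the Day 14 evening dose, before the Day 15 classroom. The protocol's clinical prohibition stays as it is. The sponsor should reconcile protocol 10.3.1 with inclusion 4 on methylphenidate before washout.

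The cost is table wording and a date filter on data already collected: medication dates are on the CRF (protocol 10.3) and screens are recorded by visit. There are three downsides. The important-deviation summary changes slightly. The CRF holds medication dates, not times, so a drug started on the evening of Day 15 would still exclude. An EOS positive does not date the use, so a few children who used a substance before Day 15 may stay in PP.

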5. DEMOGRAPHICS AND BASELINE CHARACTERISTICS

Demographics and baseline characteristics including sex, race, ethnicity, age (both continuous and categorized: 6-9 years and 10-12 years), baseline weight (kg), height (cm), and BMI (kg/m^2) will be summarized by treatment group and overall for the safety and ITT populations. Sex, race, age group, and ethnicity will be summarized using summary statistics (n and percentage) for categorical variables. Age, baseline height, baseline weight, and baseline BMI will be summarized using summary statistics (n, mean, standard deviation, median, minimum, and maximum) for continuous variables. Demographic and baseline characteristics will also be provided in a listing by subject.

5.1 Prior, Concomitant, and Post-Treatment Medications

Prior medications are defined as the following:

- Medications with a start date prior to the first date of study drug.

Concomitant medications are defined as the following:

- Medications with a start date prior to the first date of study drug and with a stop date after the first date of study drug, or
- Medications with a start date prior to the first date of study drug and is ongoing, or
- Medications with a start date on or after the first date of study drug.

Post treatment medications are defined as the following::

- Medications with a start date after the last dose of study drug, or
- Medications with a start date on or prior to last date of study drug and is ongoing, or
- Medications with a start date on or prior to last date of study drug and stop date after last date of study drug

All medications will be coded using World Health Organization drug dictionary (WHO DRUG E, 2016 Q1 version). Medications with partial start and/or end dates will be described as prior, concomitant, or post-treatment medications by using available non-missing information. Medications with completely missing start dates (i.e., missing information for medication start day, month, and year) are assumed to be both prior and concomitant medications.

The frequency and percentages of subjects using prior, concomitant, and post-treatment medications at any stage of the study will be summarized according to the WHO-DD Anatomical Therapeutic Chemical (ATC) classification Level 2 and preferred

term, by treatment group for the safety population. The ATC levels will be presented in decreasing order of the total number of subjects (frequency). The ATC levels with the same frequency will be presented alphabetically. Preferred terms within each ATC level will be presented in decreasing order of the total number of subjects (frequency). The prior and concomitant medications will also be presented in listings by subject.

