15.3.6.6. Concomitant Medications

All medications will be coded using World Health Organization drug dictionary (WHO-DD).

The prior medications will include medications started prior to the first dose date of study drug. The concomitant medications will include medications started on or after the first dose date of study drug.

Frequency counts and percentages of previous and concomitant medications will be presented by the WHO-DD Anatomic Therapeutic Chemical (ATC) classification and preferred term for each subject group.

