12.2 Changes in the Analysis Planned in the Protocol

No changes are planned as of the date of the SAP.

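### SAP 5.1 counts a drug with a completely missing start date as concomitant even when its recorded stop date is before the first dose, which its own definition rules out

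*SAP*

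**What the plan says.** SAP 5.1 calls a drug prior if it started before the first date of study drug. It gives three routes to concomitant: started before that date and stopped after it; started before that date and still ongoing; or "Medications with a start date on or after the first date of study drug".

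Two rules then deal with incomplete dates. For partial dates: "Medications with partial start and/or end dates will be described as prior, concomitant, or post-treatment medications by using available non-missing information". For completely missing start dates: "i.e., missing information for medication start day, month, and year) are assumed to be both prior and concomitant medications". This second rule does not mention the stop date.

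The results are tabulated by treatment group in the safety population, and prior and concomitant drugs are listed by subject. Protocol 10.3 has both start and stop dates recorded on the CRF.

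Protocol 15.3.6.6 divides drugs by start date alone. Those started before the first dose are prior; for the rest, "The concomitant medications will include medications started on or after the first dose date of study drug". On departures from the protocol's analysis, SAP 12.2 states: "No changes are planned as of the date of the SAP".

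**The concern.** A known stop date before the first dose settles the matter: the drug was not taken together with study drug. The missing-start rule ignores that fact and reports the drug as concomitant.

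Methylphenidate is the natural example. Protocol 8.1 requires at least 6 weeks of it before Day -7, and Protocol 10.3.1 has every child stop it 3 to 5 days before Day -1. Each child should therefore have a methylphenidate record that ended before dosing. If the start date was never captured, a correct washout appears in the by-arm table as concomitant stimulant use.

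Separately, the SAP has changed what counts as concomitant without saying so. A reader who relies on SAP 12.2 would take the table to follow the protocol's definition.

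**Working it through.** The documents give no figure to reproduce. The check applies the rules as written.

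**Step 1. Can a drug stopped before the first dose be concomitant?** Let S be the start date, E the stop date and F the first dose date, with E < F. A drug cannot start after it stops, so S ≤ E < F.

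- Route 1 needs S < F and E > F. It fails because E < F.
- Route 2 needs the drug to be ongoing. It fails because there is a stop date.
- Route 3 needs S ≥ F. It fails because S < F.

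No possible S makes the drug concomitant. It is prior only, under SAP 5.1 and under Protocol 15.3.6.6 alike.

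**Step 2. The rules applied to test records** (first dose Day 1, last dose Day 14; prior and concomitant classes only):

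| Start | Stop | SAP 5.1 as written | With the fix |
|---|---|---|---|
| Day -40 | Day -5 | prior | prior |
| missing | Day -5 | prior + concomitant | prior |
| missing | ongoing | prior + concomitant | prior + concomitant |
| Day -10 | ongoing | prior + concomitant | prior + concomitant |
| Day 2 | Day 3 | concomitant | concomitant |

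Rows 1 and 2 could be the same washed-out drug. They differ only in whether the start date was written down.

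**Step 3. The boundary.** If E = F and S is missing, S < F would give prior only and S = F would give concomitant. The class is undetermined, so keeping such a record as concomitant is reasonable. The condition should therefore be a stop date not before the first dose.

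**Step 4. SAP against protocol.** Row 4, for example melatonin (exempt from the sleep-aid ban in Protocol 10.3.1) started earlier and continued, is prior only under Protocol 15.3.6.6. Under SAP 5.1 it is prior and concomitant. SAP 5.1 also adds a post-treatment class and the missing-date rules. SAP 12.2 lists none of this.

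**Step 5. Size.** With the planned 55 children per arm, each affected child adds 1/55 = 1.8 percentage points to the drug's row. In the 6 mg/day group of about 20, each adds 1/20 = 5 points. The number of records with no start day, month or year is not given and could be zero, so no total is offered.

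**The case against.** **It is a conservative convention.** SAP 8.1 likewise sets an adverse event with a wholly missing start date to the first dose date. This stands for drugs whose stop date is missing, ongoing or not before the first dose, and the fix leaves those alone. It does not stand where the stop date already excludes overlap. Protocol 15.3.6.1 itself counts a missing-start event as an AE only if the stop date is on or after the first dose or is also missing, although SAP 8.4 words this more broadly.

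**It will be rare.** Methylphenidate history is checked by clinical assessment, informant interview and available records (Protocol 7.1), and a year alone makes the date partial, so the partial-date rule applies. This stands, and it is why no count is claimed.

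**Nothing is lost from the database.** Start and stop dates are on the CRF and listings are planned. This also stands; the error is in the class and the by-arm count.

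**The protocol's wording may not be exhaustive.** That is possible, but its paired definition of prior divides drugs by start date alone, so the natural reading is a two-way split.

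**A reader might also infer that the third route needs a cutoff**, because it counts a drug first taken on Day 16. The documents do not support calling that an error. This is a safety-population table, and medications are collected through the EOS visit. With median half-lives of 56 to 84 hours (Protocol 4.2), EOS at 7 days (168 hours) is only 168/84 = 2 to 168/56 = 3 half-lives after the last dose. A cutoff at the last dose would also drop a drug started on the morning of Day 15, while the endpoint is being measured. Moving later starts to post-treatment only would take them out of the by-subject listing, which SAP 5.1 names only for prior and concomitant drugs.

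**Conclusion.** The missing-start rule is wrong in one defined situation: start day, month and year all missing, and a recorded stop date before the first dose. It then contradicts SAP 5.1's own definition. The conclusion rests on the text alone. The frequency is unknown, and the effect is confined to descriptive medication tables and listings. The primary ANCOVA has treatment, baseline score and site as its terms and is unaffected. The unlisted change of definition is a second, minor documentation error.

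Three further inferences do not hold.

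- That this rule is why use on Day 15 cannot be seen. The table's scope is use over the whole study: "The frequency and percentages of subjects using prior, concomitant, and post-treatment medications at any stage of the study will be summarized". A drug taken only on Days 2 and 3 counts as concomitant with or without the fix.
- That this table is the only by-arm view of background treatment. SAP 4.5 summarises important deviations by category, including prohibited concomitant medications, and lists all deviations by subject; SAP 3 has categorical data summarised by treatment group.
- That false protocol deviations follow. SAP 4.5 defines that deviation by the drug list in Protocol 10.3.1, from screening through EOS and subject to clinical adjudication. It does not refer to the SAP 5.1 class.

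**What to change.** In SAP 5.1, replace the missing-start rule. For a completely missing start date, class the drug as prior and concomitant if the stop date is missing, ongoing, or on or after the first dose date; if the stop date is before the first dose date, class it as prior only.

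In SAP 12.2, record that SAP 5.1 widens the concomitant definition of Protocol 15.3.6.6 to include drugs started before the first dose and continued, and that it adds a post-treatment class and rules for missing dates.

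The cost is a few lines of SAP text and one condition in the derivation of the medication class. It uses dates already collected, and no planned table or listing is lost.

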5.2 Medical History

Medical history will be coded using MedDRA Version 19.0. The count and percentage of subjects under each history term, coded by system organ class (SOC) and preferred term (PT) will be summarized descriptively by treatment group using the safety population. The SOC terms and PTs will be presented in decreasing order of the total number of subjects (frequency) who experienced each history term. System organ class terms and PTs with the same frequency will be presented alphabetically. Medical history information will also be provided in a listing by subject.

5.3 Psychiatric History

Psychiatric history will be summarized by DSM-5 and diagnosis. The count and percentage of subjects under each DSM-5 code and diagnosis will be summarized by treatment group using the safety population. The summary will be presented in decreasing order of the total number of subjects (frequency) who experienced each psychiatric diagnosis. Psychiatric history information will also be provided in a listing by subject.

